Emicizumab is intended for prophylactic use only (i.e., not to treat bleeds that have already occurred). The primary efficacy analysis, defined as comparing the number of bleeds over time for patients randomized to receive prophylactic emicizumab versus no prophylaxis will be conducted at the earliest timepoint when all randomized patients (Arms A, B, and C) have either completed 24 weeks in the study or discontinued from treatment. For Arm D, the primary efficacy analysis will be conducted after the last enrolled patient has completed 24 weeks in the study or discontinued from treatment. Therefore, there will be a range of observation periods from 6 to approximately 12 months, or longer. Randomized patients will be enrolled globally from China and other countries. At least 60 patients will be enrolled from China.

[figure not shown]
Arm D will only enroll patients from mainland China.

To obtain additional safety and efficacy data on emicizumab, patients who are randomized to Arm C (control arm with no prophylaxis) will have the opportunity after 24 weeks to switch to receive emicizumab prophylaxis at the 6 mg/kg Q4W dosing regimen (emicizumab prophylaxis at 3 mg/kg QW subcutaneously for 4 weeks, followed by 6 mg/kg Q4W). This regimen was chosen to enhance the safety and efficacy data obtained on this dosing regimen because there will be less data available on this regimen from the global studies than from the 1.5 mg/kg QW regimen.

After completing at least 24 weeks of treatment with prophylactic emicizumab, patients who receive emicizumab prophylaxis (Arms A, B, or C after treatment switch and Arm D)

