3.3.4 Rationale for the Primary Efficacy Analysis

For Arms A, B, and C, the objective of the primary efficacy analysis is to evaluate the clinical effect of prophylactic emicizumab compared with no prophylaxis based on the number of bleeds over time (i.e., bleed rate). As mentioned in Section 3.1, the primary analysis will take place at the earliest timepoint when all randomized patients have either completed 24 weeks of treatment or discontinued from the study. This will lead to a range of observation periods from 6 to 12 months or longer in the prophylactic

emicizumab arm and is deemed to be sufficient to reliably assess the effect of prophylactic emicizumab on bleed rate reduction.

Primary efficacy analyses for Arm D will occur at the time of the last enrolled patient have completed 24 weeks in the study.

Additional efficacy analyses may be performed at the end of the study and as needed to support regulatory interactions.

In the multiple ascending dose (MAD) Phase I study (ACE001JP) involving Japanese patients with hemophilia A, a reduction in median ABR to 0 after 12 weeks of treatment (approximately 3 months) in the 1 and 3 mg/kg/wk emicizumab dose cohorts was demonstrated. In the Japanese Phase I/II extension study (ACE002JP), the median ABR of the 1 and 3 mg/kg/wk dose cohorts continued to remain zero in patients who continued to receive prophylactic emicizumab after a minimum of 24 weeks, which is consistent with evidence suggesting longer duration of prophylactic therapy is associated with maintenance of ABR reduction (Antunes et al. 2014). Patients in the 1 and 3 mg/kg/wk cohorts in Study ACE001JP/Study ACE002JP have been observed for at least 72 and 48 weeks, respectively, except for 1 patient in the 3 mg/kg/wk group who has only been followed for 44 weeks as of the cutoff date (17 April 2015).

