5.3.1 Adverse Event Reporting Period

Investigators will seek information on adverse events at each patient contact. All adverse events, whether reported by the patient or noted by study personnel, will be recorded in the patient's medical record and on the Adverse Event eCRF.

After informed consent has been obtained but prior to randomization (randomized arms) or initiation of study drug (non-randomized arm), only serious adverse events caused by a protocol-mandated intervention (e.g., invasive procedures such as biopsies, discontinuation of medications) should be reported (see Section 5.4.2 for instructions for reporting serious adverse events).

After randomization (randomized arms) or initiation of study drug (non-randomized arm), all adverse events will be reported until the patient completes his or her last study visit. After this period, the investigator should report any serious adverse events that are believed to be related to prior study drug treatment (see Section 5.6).

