6.5 SAFETY ANALYSES

The safety analyses population will be based on all enrolled patients grouped according to the actual treatment received. For Arm C patients, all safety data reported up to the day prior to switching will be included in the "control arm" safety summaries, and all safety data reported on or after the date of switching to active treatment will be reported separately.

Safety will be assessed for Arms A, B, and C and separately for Arm D through descriptive summaries of adverse events, laboratory test results (serum chemistry and hematology, including complete blood count with differential), ECGs, vital signs, and antibodies to emicizumab and FVIII.

To evaluate the overall safety of prophylactic emicizumab compared with no prophylaxis, the incidence of adverse events will be summarized and presented by System Organ Class mapped term, appropriate thesaurus level, and toxicity grade for each treatment arm.

For clinical laboratory data, summary statistics will be presented by treatment arm. In addition, shift tables describing changes from baseline will be presented using the WHO toxicity grading scale.

Data on the effect of immunogenicity (anti-emicizumab antibodies) on safety, efficacy, and/or clinical pharmacology and pharmacokinetics will be summarized adopting standard language/terminology (Shankar et al. 2014).

Although this is an open-label study, Sponsor personnel will not have access to safety summaries by treatment arm prior to the formal reporting of the study results. HCPs at participating study sites, as well as the Sponsor's drug safety and medical monitoring staff, will have access to the treatment assignments of patients for safety monitoring purposes only.

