## 4. **STATISTICAL METHODS**

### 4.1 **OUTPUT LAYOUTS**

The key output layouts are designed to address the study objectives in a flexible manner and provide an overall view of the efficacy and safety of emicizumab. In particular, patients in Arm C are allowed to switch to receive emicizumab after the first 24 weeks in the study, yielding two “study periods” (i.e., when they receive no prophylaxis for the first 24 weeks [no prophylaxis period, designated Arm Ccontrol] and emicizumab prophylaxis thereafter [emicizumab period, designated Arm Cemi]). These two periods are analyzed separately, and either period can be displayed on outputs together with the other treatment arms.

The three key output layouts are:

- **Randomized patients:** comparison of either emicizumab 1.5 mg/kg/wk (Arm A) versus no prophylaxis (control arm [Arm Ccontrol]) prior to switch to emicizumab) or emicizumab 6 mg/kg/4wks (Arm B) versus no prophylaxis (Arm Ccontrol), within a single output produced for all comparisons involving arms A, B, and C prior to switch (Arm A versus Arm Ccontrol and Arm B versus Arm Ccontrol); these outputs form the core set of the efficacy comparisons and will be supported by a corresponding safety analysis. Randomized patients will be used to describe the baseline characteristics and study conduct
- **All emicizumab patients:** these outputs will provide an overall view of all data collected under emicizumab prophylaxis (including control arm patients after switch [Arm Cemi]) and will include analyses of safety and descriptive efficacy
- **Intra-patient comparisons:** for evaluations of the change in the number of treated bleeds and all bleeds over time compared with the patient’s historical bleed rate, only patients who participated in the NIS BH29768 are included

Of note, patients may be allowed to up-titrate their emicizumab dose as described in Section 2. The data under the new, higher dose are analyzed and reported separately. Additional summaries will be produced for key safety and exposure on all data (i.e., data before and after up-titration). Note, with longer follow-up or in case up-titration occurs more frequently than expected, outputs on all data may form the core analysis and additional summaries will be produced by dose.

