#### **4.5.4 Sensitivity Analyses**

The sensitivity analyses will include different methods to define bleeds or eligible bleed data and different statistical models.

Different ways to define bleeds or eligible bleed data for A versus C and B versus C randomized comparisons:

- Include all bleeds recorded by patients in the electronic patient-reported outcomes device (i.e., without the 72-hour rule)
- Include treated joint bleeds defined as treated bleeds where the bleed type is “joint,” regardless whether any symptoms have been observed
- Include only patients who received at least 12 weeks of emicizumab treatment (if needed)
- Count days when treatment for bleeds was administered instead of the bleeds themselves
- Include only the first 24 weeks of efficacy period in the analysis. Patients who withdraw from study treatment are included up to the point of study treatment withdrawal.

Different statistical models for the bleed rate:

- An alternative NB modeling approach (using the GENMOD procedure) for the primary endpoint in which the A versus C and B versus C randomized comparisons are tested using separate models, including in the first model only the data for patients randomized into arms A and C and in the second model only the data for patients randomized into arms B and C.
- Analysis of variance (ANCOVA)
- Van Elteren test (calculated ABR)

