### **4.7.2 Adverse Events**

Adverse events will be summarized and presented by System Organ Class mapped term, appropriate thesaurus level, and toxicity grade (WHO Criteria) for each treatment arm. All adverse events will be coded using the current version of MedDRA at time of database closure. The total number and percentage of patients with at least one adverse event and total number of adverse events will be summarized. Separate adverse event summaries for serious adverse events, adverse events of special interest, severity, relatedness, and discontinuation/modification will be provided.

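### The randomised adverse-event tables compare crude percentages for Arms A and B over an expected 6 to 12 months or longer with control data that end at the switch offered after 24 weeks

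*SAP*

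**What the plan says.** SAP 4.7.2 presents adverse events for each treatment arm and states the measure: "The total number and percentage of patients with at least one adverse event and total number of adverse events will be summarized". It adds separate summaries for serious events, events of special interest, severity, relatedness and discontinuation. It gives no time window and no exposure-based rate.

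The tables are meant to be compared across arms. Protocol 6.5 states the purpose: "To evaluate the overall safety of prophylactic emicizumab compared with no prophylaxis, the incidence of adverse events will be summarized". SAP 4.1, describing the layout of Arms A and B against pre-switch Arm C, says "these outputs form the core set of the efficacy comparisons and will be supported by a corresponding safety analysis". Safety Population 1 (SAP 4.2.5) puts Arms A and B beside Arm C from the Week 1 visit, without a time limit.

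The observation periods differ by design:

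- **Control.** Under Protocol 6.5, "all safety data reported up to the day prior to switching will be included" in the control summaries, and later data are reported separately. Under Protocol 3.1, Arm C patients "will have the opportunity after 24 weeks to switch to receive emicizumab prophylaxis".
- **Arms A and B.** Under Protocol 5.3.1, "all adverse events will be reported until the patient completes his or her last study visit". On the timing of the primary analysis, Protocol 3.3.4 says: "This will lead to a range of observation periods from 6 to 12 months or longer in the prophylactic" emicizumab arm.

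For bleeds, the SAP does deal with unequal time. The negative binomial model in 4.5.1 carries the length of the efficacy period as an offset, and 4.5.4 lists a sensitivity analysis: "Include only the first 24 weeks of efficacy period in the analysis". Neither is extended to safety.

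**The concern.** The chance that a patient has at least one adverse event rises with time observed. If one arm is observed for 24 weeks and the others for longer, the percentages differ even when the drug does nothing. This is the only randomised safety comparison in the trial, and its columns would not be comparable. The direction is predictable: emicizumab looks less safe relative to no prophylaxis than it is. Totals of events are affected in the same way, and by arm size as well.

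A smaller instance of the same problem is in SAP 4.5.3. Days hospitalised are presented by treatment arm with confidence intervals but with no time unit.

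**Working it through.** The plan states no figure for this comparison, so there is none to reproduce. The check asks what the planned statistic would show if risk were identical in every arm.

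**Inputs from the documents.** Control is observed to the switch at about 24 weeks (Protocol 3.1 and 6.5). Arms A and B are observed for 6 to 12 months or longer (Protocol 3.3.4). Planned arm sizes are 28, 28 and 14 (SAP 2.4).

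**Assumptions.** The hazard is the same and constant in all arms. Control is observed for exactly 24 weeks. Follow-up T in Arms A and B is uniform over 24 to 48 weeks (mean 36). The 24-week risks p are illustrative.

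**Formula.** The cumulative hazard at 24 weeks is H = −ln(1 − p), and the weekly hazard is h = H/24. The expected percentage in Arms A and B is the mean of 1 − exp(−hT). For T uniform over 24 to 48 weeks this equals 1 − [(1 − p) − (1 − p)²]/H.

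- p = 0.10: 1 − (0.90 − 0.81)/0.1054 = 0.146
- p = 0.30: 1 − (0.70 − 0.49)/0.3567 = 0.411
- p = 0.50: 1 − (0.50 − 0.25)/0.6931 = 0.639
- p = 0.90: 1 − (0.10 − 0.01)/2.3026 = 0.961

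**Sensitivity to the assumptions**, for a 24-week risk of 10%, 30% and 50%:

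| Scenario | Control shows | Arms A/B show |
|---|---|---|
| Base: uniform 24–48 weeks | 10 / 30 / 50% | 14.6 / 41.1 / 63.9% |
| Longer: uniform 24–52 weeks | 10 / 30 / 50% | 15.3 / 42.7 / 65.7% |
| Shorter: uniform 24–36 weeks | 10 / 30 / 50% | 12.3 / 35.9 / 57.7% |
| Half the 24-week hazard in weeks 0–4, then 0.5H/20 per week; 24–48 weeks | 10 / 30 / 50% | 12.8 / 37.0 / 59.1% |
| Half of control never switches; 24–48 weeks | 12.3 / 35.6 / 57.0% | 14.6 / 41.1 / 63.9% |

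The last row takes control as 0.5 × p plus 0.5 × the Arm A/B value.

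**Event totals.** At equal rates, one emicizumab arm against control gives (28 × 36)/(14 × 24) = 1008/336 = 3.0. Of this, 28/14 = 2.0 is arm size and 36/24 = 1.5 is time.

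**Would patient-year rates be enough?** Under a constant hazard they remove the distortion. Under the early-clustering scenario they do not. The 36-week cumulative hazard is H × (1 + 0.025 × 12) = 1.3H, so the 36-week rate relative to the 24-week rate is (1.3/36)/(1/24) = 0.87. Full-period rates would then make emicizumab look better than control at equal risk. Under equal hazards, a common 24-week window gives the same expected percentage in every arm whatever the shape of the hazard over time.

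**The case against.** The strongest reply is that the gap is modest and visible. SAP 4.7 is descriptive and tests nothing. SAP 4.3 reports observation time and 4.7.1 reports duration of exposure, so a reader can see the imbalance. The error runs against emicizumab, so it cannot give false reassurance relative to control. With 14 control patients, one patient is 1/14 = 7.1 points, which exceeds the base-case excess at 10% risk. Data after up-titration are reported separately (SAP 4.1), which shortens follow-up for some Arm A and B patients. SAP 4.7.2 states no window for any arm. That Arms A and B run to the cutoff is inferred from Protocol 3.3.4 and 5.3.1, because the explicit cutoff rule in SAP 2.3.1.1 is for efficacy only.

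Much of this is fair and limits the size. It does not remove the point. Reporting follow-up elsewhere does not correct the adverse-event percentages, and drug exposure supplies no denominator for an untreated control. Up-titration is available only after at least 24 weeks on emicizumab (Protocol 4.3.2), so it cannot bring those patients down to the control window. The inference about Arms A and B is well supported, and the missing window in 4.7.2 is the gap itself.

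The hospital-days point is peripheral. Protocol 4.5.7.4, which says the days come from the eCRF, is worded for children. For school and work days, a problem arises only if they are summed across visits.

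**Conclusion.** The concern holds. Followed as written, the plan produces a randomised safety comparison in which length of observation is confounded with arm, and at equal risk it overstates adverse events on emicizumab. In the base case the excess is about 5, 11 and 14 percentage points at 24-week risks of 10%, 30% and 50%. Across the three less favourable scenarios it falls to about 2–3, 6–7 and 7–9 points. It is also small for events that nearly every patient has (90% shows as 96%).

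The omission is certain from the text. The size is not, because the documents give neither an adverse-event rate nor a follow-up distribution for this trial. Interpretation is affected, not a hypothesis test, so this should be corrected but does not threaten the trial's primary conclusion.

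**What to change.** In SAP 4.7.2, make the comparison of Arms A and B with Arm C a table restricted to the first 24 weeks in all three arms. Count events with onset from the Week 1 visit to Day 168 (24 × 7), ending earlier at switch or withdrawal, and show percentages of each arm. Do this for all adverse events, serious adverse events and adverse events of special interest.

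- Give events per patient-year over the full period as a supplement, with a note that it assumes a constant rate.
- Add a footnote that Arms A and B have adverse-event visits at Weeks 2, 3, 4 and 7 that Arm C lacks (Protocol Appendix 1-A). The common window does not remove that difference in ascertainment.
- Keep the crude all-data table for the All Emicizumab output.
- In SAP 4.5.3, report days hospitalised over the first 24 weeks or per 24 weeks. Use the same window for school and work days if they are summed across visits.

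The cost is a few extra tables from data already collected, with no new data and no protocol change.

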### **4.7.3 Laboratory Data**

For clinical laboratory data that were collected from local laboratories, summary statistics in International System of Units (SI) will be presented by treatment arm. Laboratory data not collected in SI units will be converted to SI units as applicable. In addition, shift tables describing changes from baseline will be presented using the WHO toxicity grading scale.

Data on the impact of immunogenicity (anti-emicizumab antibodies) on safety, efficacy, and/or clinical pharmacology and pharmacokinetics will be summarized using standard language/terminology ([Shankar et al. 2014](#)).

#### **4.7.4 Vital Signs**

Vital signs will be summarized by treatment arm using mean change from baseline tables over time. Measurements consist of heart and respiratory rate, temperature, and systolic and diastolic blood pressures.

#### **4.7.5 Electrocardiogram**

ECG results and corresponding changes from baseline will be summarized by treatment arm and visit for QT, RR, HR, QTcB, QTcF, PR, and QRS and T- and U-wave morphology.

### **4.8 EXPLORATORY BIOMARKER ANALYSES**

PD parameters (e.g., aPTT, parameters derived from thrombin generation, FVIII activity) and markers related to bone and joint health will be presented using summary statistics over time, including arithmetic and geometric means, median, range, standard deviations, and coefficients of variation. Summary and individual patient plots will also be produced, if applicable.

### **4.9 MISSING DATA**

On the electronic handheld devices, including the tablet on which the HRQoL endpoints are reported, it is not possible to leave questions unanswered or to enter partial data. Therefore the data for the primary and secondary bleed related endpoints and the HRQoL questionnaires are considered complete.

In the site data entry system, the symptoms of joint and muscle bleed are not collected. Therefore, bleeds with an anatomical location in a joint are considered joint bleeds.

### **4.10 INTERIM ANALYSES**

No efficacy interim analyses are planned.

## Appendix 1 Protocol Synopsis

**TITLE:** A RANDOMIZED, MULTICENTER, OPEN-LABEL, PHASE III CLINICAL TRIAL TO EVALUATE THE EFFICACY, SAFETY, AND PHARMACOKINETICS OF PROPHYLACTIC EMICIZUMAB VERSUS NO PROPHYLAXIS IN HEMOPHILIA A PATIENTS

**PROTOCOL NUMBER:** YO39309

**VERSION NUMBER:** 3

**TEST PRODUCT:** Emicizumab (RO5534262)

**PHASE:** Phase III

**INDICATION:** Hemophilia A

**SPONSOR:** F. Hoffmann-La Roche Ltd

### Objectives and Endpoints

This study will evaluate the efficacy, safety, and pharmacokinetics of prophylactic emicizumab compared with no prophylaxis in patients with hemophilia A. Specific objectives and corresponding endpoints for the study are outlined below.

1. Objectives	2. Corresponding Endpoints
3. Primary Efficacy Objective: 

• To evaluate the efficacy of prophylactic emicizumab (i.e., administered on a scheduled basis with the intent to prevent bleeds) compared with no prophylaxis in patients with hemophilia A The primary definition of a bleed is a bleed for which coagulation factors are administered (i.e., treated blood).

	4. Primary Efficacy Endpoint 

• The number of bleeds over time (i.e., bleed rate) The endpoint will be analyzed separately for the two emicizumab arms: 1.5 mg/kg QW and 6 mg/kg Q4W

5. Secondary Efficacy Objective: 

• To evaluate the efficacy of prophylactic emicizumab compared with no prophylaxis

• Change over time compared with historical bleed rate prior to study entry will be conducted within each treatment arm.

	6. Secondary Efficacy Endpoints 

• To evaluate the efficacy in reducing the number of all bleeds over time

• Change in the number of treated bleeds and all bleeds over time compared with the patient's historical bleed rate

• To evaluate the efficacy in reducing the number of joint bleeds over time

• To evaluate the efficacy in reducing the number of target joint bleeds over time

• Change in HRQoL of patients according to Haem-A-QoL (aged <math>\geq 18</math> years) or Haemo-QoL-Short Form (aged 12–17 years) scores after 24 weeks

• Change in health status of patients according to European Quality of Life Five-Dimension-Five Levels (EQ-5D-5L) Questionnaire scores after 24 weeks

## Appendix 1

### Protocol Synopsis (cont.)

7. Exploratory Objective:	8. Exploratory Endpoints

 
• To assess the number of days away from school/work
 
• To assess the number of days hospitalized
 
• To assess potential PD biomarkers of emicizumab
 
	
 
• Changes in number of days away from school/work during treatment
 
• Changes in number of hospitalization days during treatment
 
• PD Biomarkers of emicizumab, including but not limited to aPTT, thrombin generation, and FVIII activity
 

9. Safety Objective:	10. Safety Endpoints

 
• To evaluate the overall safety of prophylactic emicizumab compared with no prophylaxis in patients with hemophilia A
 
	
 
• The incidence and severity of adverse events
 
• The incidence and severity of thromboembolic events
 
• Incidence and severity of thrombotic microangiopathy
 
• Changes in physical examination findings and vital signs
 
• Incidence of laboratory abnormalities
 
• Incidence and severity of injection-site reactions
 
• Incidence of adverse events leading to drug discontinuation
 
• The incidence of severe hypersensitivity, anaphylaxis, or anaphylactoid reactions
 
• The incidence and clinical significance of anti-emicizumab antibodies
 

## Appendix 1

